All 0-hour (predose) samples are relative to the respective study drug administrations. The timing of blood collections will take priority over all other scheduled study activities except for dose administration. The date and time (to the nearest minute) of each blood sample collection will be recorded.

Additionally, the date and time (to the nearest minute) of each venetoclax and pomalidomide dose and whether or not the venetoclax dose was taken within 30 minutes after the completion of meal will be recorded for each scheduled PK sampling day and for the 2 doses before each scheduled PK day (if applicable). Sites will ensure all information is captured through source documents (site or subject calendar/diary provided by AbbVie).

Venetoclax Samples

Disposition of Samples

Whole blood will be collected into appropriately labeled tubes and processed as outlined in the most current version of Study M16-085 laboratory manual. An inventory of the samples included will accompany the package. Arrangements will be made with AbbVie for the transfer of samples to:

Attn: AbbVie Sample Receiving

[REDACTED]
c/o: Delivery Services
[name]
[name]

Phone:

Fax:

Email:

Measurement Method

Plasma concentrations of venetoclax will be determined by the bioanalysis department at AbbVie using a validated method. Plasma concentration of possible venetoclax metabolite(s) may be determined with validated or nonvalidated methods.

Pomalidomide Samples

Disposition of Samples

Whole blood will be collected into appropriately labeled tubes and processed as outlined in the most current version of Study M16-085 laboratory manual. An inventory of the samples included will accompany the package. Arrangements will be made with inVentiv Health Clinique, Inc. for the transfer of samples to:

Attn: Sample Receiving
inVentiv Health Clinique, Inc.
[name]
[name]

[contact]

Fax:

Email:

Measurement Method

Plasma concentrations of pomalidomide will be determined using a validated method under the supervision of bioanalysis department at AbbVie.

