- enteric-coated aspirin 81 mg PO, QD or low molecular weight heparin if history of prior thrombotic disease according to local practice

Allowed Concomitant Therapies

The following concomitant medications are allowed during the study:

- Bisphosphonates intravenous or PO as indicated per institutional guidelines. Note: institution of bisphosphonates after Cycle 2 if not already in use is prohibited.
- Only low-dose corticosteroids (e.g., prednisone \leq 10 mg PO, QD or its equivalent), inhaled steroids, and topical preparations for reasons other than MM (e.g., asthma) are allowed during the study. Systemic corticosteroids $>$ 10 mg PO QD of prednisone (or its equivalent) should not be given on the same day as dexamethasone administration. Systemic corticosteroids $>$ 10 mg PO QD of prednisone (or its equivalent) are allowed when the dose of prednisone (or its equivalent) is given for less than 7 days and the cumulative dose is $<$ 120 mg. For additional guidance and to determine the equivalent dose of systemic corticosteroid, refer to [Appendix K](#).
- Surgery and radiation:
 - Localized radiation therapy to a site of pre-existing disease may be permitted while on study. Following approval by the AbbVie Therapeutic Area Medical Director (TA MD) or designee, the subject may initiate or continue with protocol therapy without interruption during the course of palliative radiation therapy if the risk of excessive bone marrow suppression or other toxicity is acceptable, per the investigator's opinion, and the treatment is in the best interest of the subject.
 - If the subject develops a definite increase in the size of existing bone lesions or soft tissue plasmacytomas that meet the criteria for PD, treatment must be discontinued for PD regardless of whether radiation therapy is initiated.
 - Kyphoplasty, vertebroplasty, or emergency orthopedic surgery is permitted.
 - Use of radiotherapy or surgical intervention must be recorded on the eCRF.

Pretreatment Guidance

Anti-Infective Prophylaxis

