Progressive Disease: Two consecutive assessments for confirmation of PD made at any time before the start of new therapy are required per IMWG criteria ([Appendix F](#)). The second assessment may be taken immediately if PD is suspected. If PD is suspected by rising serum or urine M-protein (or FLC in subjects without measurable disease), 2 consecutive assessments from central laboratory readings should be obtained.

If PD is suspected by clinical symptoms, a plasmacytoma evaluation and/or skeletal survey should be obtained, as clinically indicated, and compared with baseline assessments to determine whether a new bone lesion or plasmacytoma has developed or an existing lesion or plasmacytoma has worsened. Serum and urine protein electrophoresis are also required.

The following assessments are not sufficient to determine PD:

- Rising serum FLC if disease is measurable in the serum, urine, or both.
- Serum FLC can be used to determine PD according to the IMWG criteria only for subjects without measurable serum and urine M-protein.
- Clinical relapse based on indicators that are not part of the IMWG criteria for PD (e.g., decrease in hemoglobin, hypercalcemia, increase in serum creatinine, hyperviscosity), and relapse from clinical relapse categories should not be considered PD.

- General worsening of the subject's condition. If a subject's condition has deteriorated to a point that remaining on protocol therapy is not an option, every effort should be made to document PD by at least one of the following assessments prior to the initiation of new therapy: serum protein electrophoresis, urine protein electrophoresis, bone marrow biopsy, plasmacytoma evaluation, or skeletal survey.

Investigators are requested not to discontinue subjects from treatment for presumed lack of response after only 1 cycle of study treatment.

Clinical Relapse: Clinical relapse is defined per IMWG criteria ([Appendix F](#)) and cannot be used to determine PD.

Evaluation of Disease

IMWG assessments will be reviewed by the investigator per the IMWG criteria ([Appendix F](#)). If the investigator confirms that the subject meets the criteria for PD by 2 consecutive assessments, the subject will be deemed as having met an event of disease progression. For the purposes of this study, the date of progression will be the date on which the IMWG assessments were obtained.

Biomarker Sampling

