Stable disease ^e	
 • Not meeting criteria for CR, VGPR, PR, MR or progressive disease
Progressive disease	
 • Any one or more of the following criteria: 
 • Increase of 25% from lowest confirmed response value in one or more of the following criteria: 
 • Serum M-protein (absolute increase must be ≥ 0.5 g/dL); • Serum M-protein increase ≥ 1 g/dL, if the lowest M-component was ≥ 5 g/dL; • Urine M-protein (absolute increase must be ≥ 200 mg/24 hr); • In patients without measurable serum and urine M-protein levels, the difference between involved and uninvolved FLC levels (absolute increase must be > 10 mg/dL); • In patients without measurable serum and urine M-protein levels and without measurable involved FLC levels, bone marrow plasma-cell percentage irrespective of baseline status (absolute increase must be $\geq 10\%$); • Appearance of a new lesion(s), $\geq 50\%$ increase from nadir in SPD^f of > 1 lesion, or $\geq 50\%$ increase in the longest diameter of a previous lesion > 1 cm in short axis; • $\geq 50\%$ increase in circulating plasma cells (minimum of 200 cells/μL) if this is the only measure of disease
Clinical relapse	
 • Clinical relapse requires one or more of the following criteria: 
 • Direct indicators of increasing disease and/or end organ dysfunction (CRAB features) related to the underlying clonal plasma-cell proliferative disorder. It is not used in calculation of time-to-progression or progression-free survival but is listed as something that can be reported optionally or for use in clinical practice; • Development of new soft tissue plasmacytomas or bone lesions (osteoporotic fractures do not constitute progression); • Definite increase in the size of existing plasmacytomas or bone lesions. A definite increase is defined as a 50% (and ≥ 1 cm) increase as measured serially by the SPD^f of the measurable lesion; • Hypercalcemia (> 11 mg/dL); • Decrease in hemoglobin of ≥ 2 g/dL not related to therapy or other non-myeloma-related conditions; • Rise in serum creatinine by 2 mg/dL or more from the start of the therapy and attributable to myeloma; • Hyperviscosity related to serum paraprotein

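### Appendix F lists new lesions under both PD and clinical relapse, and Appendix E bars clinical relapse from PD with no exception for a finding that meets both

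*Protocol*

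**What the plan says.** - **Protocol Appendix F, Progressive disease row.** PD needs "Any one or more of the following criteria", and one item on the list begins "Appearance of a new lesion(s". The row does not name the type of lesion.
- **Protocol Appendix F, Clinical relapse row.** One item is "Development of new soft tissue plasmacytomas or bone lesions"; another is a definite increase in existing ones. The first item, on direct indicators of end-organ damage, also carries the sentence "It is not used in calculation of time-to-progression or progression-free survival".
- **Protocol Appendix E, Progressive Disease.** A list of findings that do not suffice for PD has a bullet in two parts. The first part concerns clinical relapse resting on indicators outside the IMWG PD criteria, with hemoglobin, calcium, creatinine and viscosity as examples. The second part adds that "relapse from clinical relapse categories should not be considered PD".
- **Protocol Appendix E, Clinical Relapse.** This line says that clinical relapse is as Appendix F defines it "and cannot be used to determine PD". It has no qualifier.
- **Protocol Section 5.4, Surgery and radiation.** The text refers to a "definite increase in the size of existing bone lesions or soft tissue plasmacytomas that meet the criteria for PD".
- **SAP Section 4.3.2.** PFS counts the first documented PD or death. TTP and DOR count the first documented PD or death due to myeloma. The SAP gives no PD definition of its own.

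**The concern.** The same finding, a new plasmacytoma or bone lesion, stands in two adjacent rows with opposite consequences. One row makes it PD. The other makes it clinical relapse, which Appendix E excludes from PD. No sentence expressly says how to classify a finding that meets both.

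The case that matters is lesion-only progression: a new lesion while M-protein is stable. A site following the PD row records a progression, subject to confirmation. A site following the Clinical Relapse line does not, and the subject stays progression-free until a later M-protein progression, a qualifying death or censoring. Progression is judged by the investigator in an open-label study, so nothing in the documents ensures that sites read the rows alike.

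**Working it through.** No sample size, power or event count enters this point, so the check is a comparison of text.

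**Step 1: the overlap.** Lesion is read to include bone lesions and plasmacytomas, because those are what Appendix E tells sites to look for when PD is suspected from symptoms.

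| Finding, M-protein stable | PD row | Clinical relapse row | Appendix E bar read literally |
|---|---|---|---|
| New bone lesion | PD | Listed | Not PD |
| New soft tissue plasmacytoma | PD | Listed | Not PD |
| Hemoglobin fall of at least 2 g/dL, not otherwise explained | Not listed | Listed | Not PD |

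The third line shows where the bar works as intended. The first two conflict.

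**Step 2: does other text settle it?** Four places point to PD.

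1. The opening of the Appendix E bullet is confined to indicators outside the PD criteria, and none of its examples is a lesion.
2. The status categories in Appendix E are sCR, CR, VGPR, PR, MR, SD and PD; clinical relapse is not among them. Every one except PD requires that no new or advancing bone lesion be known. If the bar also removes PD, a subject with a new bone lesion has no status under Appendix E, while the stable disease row of Appendix F would take that subject by default. The Appendix E rule names only bone lesions; Appendix F footnote a adds extramedullary plasmacytomas.
3. Table 4 provides for plasmacytoma evaluation to confirm PD.
4. Appendix E directs imaging for new or worse lesions when symptoms suggest PD, and lists plasmacytoma evaluation and skeletal survey among the ways to document PD.

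Against these stand the second half of the bullet and the whole Clinical Relapse line. Neither is limited to findings outside the PD row.

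**Step 3: confirmation.** Appendix E requires two consecutive assessments for PD, which may fall on the same day but need two discrete samples; one bone marrow assessment is enough. The rule is worded for samples and does not say what a second assessment means for imaging. Even on the PD reading, it is open whether a single scan suffices.

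**Step 4: response.** Appendix E and footnote a both deny a response category when new or advancing lesions are known, whether the event is called PD or clinical relapse. Response status therefore does not turn on the disputed choice.

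**Step 5: growth of an existing lesion.** The two rows measure growth differently. Take one plasmacytoma going from 4.0 × 4.0 cm to 5.0 × 5.0 cm:

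- Product of diameters: 16 to 25 cm², 25/16 − 1 = 56%.
- Longest diameter: 4.0 to 5.0 cm, 5.0/4.0 − 1 = 25%, an increase of 1.0 cm.

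This can fit the relapse item (50% and at least 1 cm). It fails the PD items, which need 50% in the longest diameter of a lesion, or 50% in the summed products of more than one lesion. It is relapse and not PD. Two categories with different thresholds do not contradict each other; the conflict is confined to findings that meet both rows.

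**The case against.** The strongest reply is that a careful reader would reach PD anyway. The bullet opens by limiting itself to indicators outside the PD criteria, the status rules leave a known new bone lesion no home but PD, and imaging is a named way to document PD. Most of this stands, and it shows what was probably meant. It does not remove the problem. If the second half of the bullet only restates the first, it is redundant; read naturally, it takes in the whole clinical relapse row. The Clinical Relapse line has no limit at all and points to the row that contains new lesions.

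A reader might also infer stronger things that the documents do not support:

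- *That one scan can by itself end or continue PFS.* PD needs two consecutive assessments.
- *That Appendix F excludes the whole relapse row from PFS and TTP.* The excluding sentence is printed inside the direct-indicators item. Its wording could refer to clinical relapse as such, but extending it to the lesion items is an inference.
- *That ORR is at risk.* Response is barred under either label.
- *That Section 5.4 misuses a relapse term for PD.* That sentence already limits itself to growth meeting the PD criteria.

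It is also fair that PFS, TTP and DOR are secondary and are only estimated by Kaplan-Meier methods (SAP Section 6.2).

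**Conclusion.** The point holds as a contradiction in wording. Appendix F makes a new lesion PD; two statements in Appendix E, taken as written, withdraw that status because the same finding is also listed as clinical relapse. The weight of the surrounding text favors PD, but sites could still classify the same lesion-only finding differently.

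The reach is PFS, TTP and DOR. The ORR tests and the sample sizes are not shown to be affected, and no stated figure changes. The number of subjects concerned cannot be estimated, because the documents give neither a lesion-only progression rate nor an expected number of progressions. The conclusion assumes that the PD row's new lesion covers bone lesions and plasmacytomas. The correction should be made, but it does not call the design into question.

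**What to change.** 1. In Appendix E, amend the Clinical Relapse line and the second half of the bullet. State that a finding meeting any criterion in the PD row counts as PD for PFS, TTP and DOR even if it is also listed under clinical relapse, and that the bar applies only to findings meeting no PD-row criterion.
2. Put a matching note beside the Clinical relapse row of Appendix F.
3. State in Appendix E how the two-assessment rule applies to PD found on imaging, and which date is then the progression date.
4. Check that the wording of Sections 5.4 and 5.5 agrees with the PD row. This asks only for reconciliation and proposes no rule on stopping treatment or withdrawal.

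The cost is a few sentences of protocol text, with no new assessments unless the sponsor's answer to item 3 requires a second imaging assessment. The downside is that some secondary-endpoint events may be dated earlier than under the literal bar.

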APPENDIX F. IMWG RESPONSE CRITERIA FOR MULTIPLE MYELOMA (2016)

Response Subcategory	Response Criteria ^a
Stringent complete response*	
 Negative immunofixation on the serum and urine (regardless of whether disease at baseline was measurable in serum, urine, both, or neither) and Disappearance of any soft tissue plasmacytomas and < 5% plasma cells in bone marrow^b and Normal FLC ratio** and Absence of clonal cells in bone marrow^b by immunohistochemistry (κ/λ ratio $\leq 4:1$ or $\geq 1:2$ for κ and λ patients, respectively, after counting ≥ 100 plasma cells)^c
Complete response* ^c	
 Negative immunofixation on the serum and urine (regardless of whether disease at baseline was measurable on serum, urine, both, or neither) and Disappearance of any soft tissue plasmacytomas and < 5% plasma cells in bone marrow^b and For subjects in whom the only measurable disease is by serum FLC levels, a normal FLC ratio** is also required
Very good partial response*	
 Serum and urine M-protein detectable by immunofixation but not on electrophoresis or $\geq 90\%$ reduction in serum M-protein plus urine M-protein < 100 mg per 24 hours For subjects in whom the only measurable disease is by serum FLC levels, VGPR is defined as: 
 $\geq 90\%$ decrease in the difference between involved and uninvolved FLC levels
Partial response	
 $\geq 50\%$ reduction of serum M-protein and Reduction in 24-hour urinary M-protein by $\geq 90\%$ or to < 200 mg per 24 hours 
 If the serum and urine M-protein are unmeasurable,^d a $\geq 50\%$ decrease in the difference between involved and uninvolved FLC levels is required in place of the M-protein criteria If the serum and urine M-protein are unmeasurable,^d and serum-free light assay is also unmeasurable, a $\geq 50\%$ reduction in plasma cells is required in place of M-protein provided baseline bone marrow plasma-cell percentage was $\geq 30\%$ $\geq 50\%$ reduction in the size of soft tissue plasmacytomas is also required, if present at baseline
Minimal response	
 25% – 49% reduction of serum M-protein and 50% – 89% reduction in 24-hour urinary M-protein and $\geq 50\%$ reduction in the size (SPD)^f of soft tissue plasmacytomas if present at baseline

Response Subcategory	Response Criteria ^a
Stable disease ^e	
 • Not meeting criteria for CR, VGPR, PR, MR or progressive disease
Progressive disease	
 • Any one or more of the following criteria: 
 • Increase of 25% from lowest confirmed response value in one or more of the following criteria: 
 • Serum M-protein (absolute increase must be ≥ 0.5 g/dL); • Serum M-protein increase ≥ 1 g/dL, if the lowest M-component was ≥ 5 g/dL; • Urine M-protein (absolute increase must be ≥ 200 mg/24 hr); • In patients without measurable serum and urine M-protein levels, the difference between involved and uninvolved FLC levels (absolute increase must be > 10 mg/dL); • In patients without measurable serum and urine M-protein levels and without measurable involved FLC levels, bone marrow plasma-cell percentage irrespective of baseline status (absolute increase must be $\geq 10\%$); • Appearance of a new lesion(s), $\geq 50\%$ increase from nadir in SPD^f of > 1 lesion, or $\geq 50\%$ increase in the longest diameter of a previous lesion > 1 cm in short axis; • $\geq 50\%$ increase in circulating plasma cells (minimum of 200 cells/μL) if this is the only measure of disease
Clinical relapse	
 • Clinical relapse requires one or more of the following criteria: 
 • Direct indicators of increasing disease and/or end organ dysfunction (CRAB features) related to the underlying clonal plasma-cell proliferative disorder. It is not used in calculation of time-to-progression or progression-free survival but is listed as something that can be reported optionally or for use in clinical practice; • Development of new soft tissue plasmacytomas or bone lesions (osteoporotic fractures do not constitute progression); • Definite increase in the size of existing plasmacytomas or bone lesions. A definite increase is defined as a 50% (and ≥ 1 cm) increase as measured serially by the SPD^f of the measurable lesion; • Hypercalcemia (> 11 mg/dL); • Decrease in hemoglobin of ≥ 2 g/dL not related to therapy or other non-myeloma-related conditions; • Rise in serum creatinine by 2 mg/dL or more from the start of the therapy and attributable to myeloma; • Hyperviscosity related to serum paraprotein

CR = complete response; CRAB = calcium elevation, renal failure, anemia, lytic bone lesions; CT = computed tomography; FLC = free-light chain; IMWG = International Myeloma Working Group; M-protein = monoclonal-protein; MR = minimal response; MRI = magnetic resonance imaging; PET = positron emission tomography; PR = partial response; SPD = sum of the products of the maximal perpendicular diameters of measured lesions; VGPR = very good partial response

- a. All response categories require 2 consecutive assessments made at any time before the institution of any new therapy; all categories also require no known evidence of progressive or new bone lesions or extramedullary plasmacytomas if radiographic studies were performed. Radiographic studies are not required to satisfy these response requirements.
- b. Confirmation with repeat bone marrow biopsy not needed.
- c. Presence/absence of clonal cells on immunohistochemistry is based upon the k/λ ratio. An abnormal k/λ ratio by immunohistochemistry requires a minimum of 100 plasma cells for analysis. An abnormal ratio reflecting presence of an abnormal clone is k/λ of > 4:1 or < 1:2.
- d. Measurable disease is defined as meeting at least one of the following 3 measurements: serum M-protein ≥ 1 g/dL (≥ 10 g/L) or urine M-protein ≥ 200 mg/24 hours or serum FLC assay with an involved FLC level ≥ 10 mg/dL (≥ 100 mg/L) provided serum FLC ration is abnormal.
- e. Not recommended for use as an indicator of response; stability of disease is best described by providing the time to progression estimates.
- f. Plasmacytoma measurements should be taken from the CT portion of the PET/CT, or MRI scans, or dedicated CT scans where applicable. For patients with only skin involvement, skin lesions should be measured with a ruler. Measurement of tumor size will be determined by the SPD.

Notes:

- * Clarification to IMWG criteria for coding CR and VGPR in subjects whom the only measurable disease is by serum FLC levels. In these subjects, CR is defined as a normal FLC ratio of 0.26 to 1.65 in addition to CR criteria listed above, and VGPR is defined as a ≥ 90% decrease in the difference between involved and uninvolved FLC levels.
- ** Serum and urine M-protein testing is required to fulfill requirements of VGPR and CR categories regardless of whether disease at baseline was measurable in serum, urine, both, or neither.

